**Table 4. Schedule of Events**

Procedures	Baseline Visit 1	BMAC Injection Visit 2	Amp Day Visit 3	Day 3 F/U + 5 days Visit 4	Week 2 F/U +/- 2 days Visit 5	Week 6 F/U +/- 4 days Visit 6	Week 12 F/U +/- 7 days Visit 7	Week 18 F/U +/- 2 weeks Visit 8	Week 24 F/U +/- 2 weeks Visit 9	Week 52 Phone Call
Informed Consent	X									
Medical History	X									
Physical Exam	X	X	X	X	X	X	X	X	X	
Vital Signs	X	X	X	X	X	X	X	X	X	
Con. Medications	X	X	X	X	X	X	X	X	X	
AE/SAE Evaluations		X	X	X	X	X	X	X	X	
Laboratory evaluations	X 				X 	X 	X 	X 	X 	
12 Lead ECG	X				X		X		X	
LEADs / TcPO2	X 				X 	X 	X 	X 	X 	
Photograph of index leg / amputation site	X 				X 	X 	X 	X 	X 	
Schedule Amputation	X									
Research Blood Specimen 		X	X		X	X	X	X	X	
Evaluate for infection, gangrene				X	X	X	X	X	X	X
Evaluate necessity for amputation revision				X	X	X	X	X	X	X
Screening Laboratory Tests: CBC w/diff/plt; CMP (Sodium, Potassium, Chloride, CO2, Glucose, Calcium, BUN, Creatinine); eGFR, hsCRP										
Baseline only: Serum pregnancy testing (childbearing females)										
Follow-up labs: hsCRP										
TcPO2: Transcutaneous Oxygen Pressure; LEADs or Foot TcPO2  will be collected as a baseline measurement, TcPO2 of medial and lateral stump site  will be collected at follow up visits										
Photographs: Index leg at baseline  , BKA stump site at follow up visits  . It is not considered a protocol deviation if photographs were not performed.										
Research blood specimens: Collected prior to induction of surgery (BMAC Injection Day, and Amputation Day) from peripheral vein of up to 30 mL, and at follow-up visits at weeks 2 through week 24. It is not considered a protocol deviation if research blood collection is not performed.										

## **7.2 Study Data**

Eligible subjects will be invited to participate in the study on a first-come basis. Potential donors must provide informed consent to participate. To be eligible for participation, subjects must be at least 40 years of age.

### **7.2.1 Collection of data**

At the discretion of the Investigator and subject to Indiana University School of Medicine requirements, data will be collected from each eligible subject providing signed informed consent.

## **7.3 Procedures for Study Closure**

### **7.3.1 Routine study close-out**

The study will end when Indiana University School of Medicine has obtained all data necessary to complete its studies of the test product. Study close-out will follow Indiana University School of Medicine standard procedures and may include, but is not limited to, review of regulatory documents, collection of completed case report forms, reconciliation of study records, removal or destruction of ancillary study supplies, and informing the Investigator of remaining obligations (e.g., record retention, final report submission to the IRB, financial disclosure updates, etc.).

### **7.3.2 Suspension or premature termination of the study**

This study may prematurely terminate at any time because of a regulatory authority decision, a change in opinion of the IRB, or at the discretion of the Investigator or Sponsor. The study will be terminated in the event of a Grade 4-5 unexpected and research related event based on the Common Terminology Criteria for Adverse Events (CTCAE), version 4.0. Enrollment will be temporarily suspended for any related or possibly related post-BMAC injection and post-amputation infection, bleeding or tissue reaction at the index site that are  $\geq$  Grade 3. If this trial is temporarily suspended or prematurely discontinued, Indiana University School of Medicine will promptly notify the Investigator(s) and provide instructions. If the study is temporarily suspended, Indiana University School of Medicine will provide guidance on timing and procedures for resuming the study. If the study is prematurely discontinued, all study materials must be collected and all study forms completed to the extent possible. All such materials must be returned to Indiana University School of Medicine upon request with an explanation of the circumstances that led to termination.

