### **9.3 Planned Analyses**

The clinical study report will contain only summary data analyses reflecting safety profiles, and summary data analyses of efficacy. All patient data will remain coded during analyses to maintain patient confidentiality.

The data management center for this trial will be at the CTSI, or a Data Monitoring Committee (DMC) will be appointed by the Principal Investigator. We will use a web-based HIPAA compliant online system for data entry and data management, as we are currently doing in our current clinical trials. Data will be collected from each enrolled patient using a comprehensive case report form and uploaded into a specifically designed database in the OnCore Enterprise Clinical Trial Management System and VA REDCap system. All the data will be analyzed and generated using SAS.

**Safety Assessment.** Primary attention will focus on the safety of the administration of BMAC as measured by treatment-related AEs. Treatment-related AEs will be categorized overlapping systems and severities. Three categories of systems are cardiovascular, respiratory, or infectious. Two categories of severity will be serious adverse (SAE) and major adverse cardiac events (MACE). For completeness, instances of AEs may appear in more than one category. Within each of these categories AEs will be listed in descending order of frequency for the treatment group. In addition, for each category, the sum and difference between the two routes of delivery of the proportions will be reported as percent incidence. Binomial confidence Intervals at the 95% confidence level and *p*-values for these 3 groups will be calculated. Since previous trials have not reported AEs with BMAC treatment, confidence intervals will be generated by the method of the Wilson Score Interval because they are robust, with good coverage probability even for small number of trials and are not degenerate near zero. These intervals will be used to summarize the data rather than as any formal inferential statement and to assist the Data Monitoring Board in their deliberations. No adjustment for multiplicity will be made.

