## **10 ADVERSE EVENT REPORTING**

### **10.1 Adverse Events**

Reporting of adverse events will comply with federal regulations for IDE safety reporting. AEs occurring during the enrollment period should be documented by the Investigator in progress notes but will not

be collected or analyzed by Indiana University School of Medicine unless considered serious and research related by the Investigator. The MedDRA scale will be used to describe adverse events.

Serious adverse events (SAEs) related to the research treatment that are encountered during study enrollment will be documented by the Investigator and reported to Indiana University School of Medicine within 72 hours upon discovery. SAEs are defined under current cGCP guidelines as events that result in one or more of the following:

- life-threatening illness or injury;
- permanent impairment of a body structure or a body function;
- medically necessary in-patient hospitalization;
- medical or surgical intervention necessary to prevent permanent impairment to body structure or function; or
- fetal distress, fetal death, or congenital abnormality.

Serious events that affect the rights, safety, or welfare of subjects must be documented on a form and be reported within 72 hours to Indiana University School of Medicine and to the Investigator's IRB according to that IRB's policies.

Any potential deficiencies with the BioCue™ devices (including, but not limited to deficiencies in packaging, labelling, and/or device processing) will be reported to Zimmer Biomet for evaluation.

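### A non-serious Grade 3 bleed or tissue reaction can suspend enrollment under Section 7.3.2 yet be left out of the sponsor's data and the Section 9.3 safety rate

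*Combined protocol and SAP*

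**What the plan says.** Three sections of the combined protocol and SAP decide which adverse events count, each for a different purpose.

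- **Section 7.3.2 (suspension and termination).** "Enrollment will be temporarily suspended for any related or possibly related post-BMAC injection and post-amputation infection, bleeding or tissue reaction" at the index site, with a floor of CTCAE Grade 3. Seriousness is not a condition. A separate rule reads: "The study will be terminated in the event of a Grade 4-5 unexpected and research related event".
- **Section 10.1 (collection).** The investigator notes AEs in the progress notes, but they will not "be collected or analyzed by Indiana University School of Medicine unless considered serious and research related by the Investigator". The same section lists what makes an event serious. It also requires serious events bearing on subjects' rights or safety to be put on a form and reported within 72 hours, with no relatedness condition.
- **Section 9.3 (analysis).** "Primary attention will focus on the safety of the administration of BMAC as measured by treatment-related AEs". On grouping it says: "Three categories of systems are cardiovascular, respiratory, or infectious". The two severity groups are SAEs and major adverse cardiac events. Proportions get 95% Wilson score intervals, intended partly to help the monitoring board.

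No section in the text available defines treatment-related or research related, says whether possibly related counts as related, or links CTCAE grade to seriousness.

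**The concern.** Safety is the main question of this 12-subject pilot, and the treatment-related AE rate is its main safety result. One would expect any event grave enough to halt enrollment to appear in that result. The text does not secure this, for three reasons.

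- Section 10.1 filters on seriousness, and Section 7.3.2 does not.
- Section 7.3.2 names possibly related events explicitly, while 9.3 and 10.1 do not say how to treat them.
- Section 9.3 has no system category for two of the three event types that 7.3.2 lists.

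If such an event dropped out, the final report could show a lower related-AE rate than the suspension history implies. Section 7.3.2 also has the sponsor guide any resumption, and it would be doing so after an event that 10.1 does not require it to collect. The monitoring board reviews treatment-related AEs and SAEs (Section 6.1.2), so its tables could also differ from the events behind a suspension.

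**Working it through.** The plan gives no expected AE rate, and its sample size is not derived from one, so there is no stated figure to reproduce. The check is to run test events through the three sections and then size the effect of one omission.

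**Step 1: the conditions side by side**

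| | 7.3.2 suspension | 10.1 sponsor collection | 9.3 safety rate |
|---|---|---|---|
| Relatedness | related or possibly related | research related | treatment-related |
| Serious? | not required | required | not required, but SAE is a severity group |
| Grade | CTCAE 3 or higher | none | none |
| Event type | index-site infection, bleeding, tissue reaction | any | cardiovascular, respiratory, infectious |

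**Step 2: test events, each Grade 3 at the index site**

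1. *Non-serious bleed or tissue reaction, judged related.* It suspends enrollment. It fails the seriousness condition in 10.1, so the sponsor does not collect it. It is treatment-related under 9.3, but fits no system category and neither severity group. The exclusion here has nothing to do with how relatedness is graded.
2. *The same event, judged possibly related.* It suspends enrollment and again fails the seriousness condition. Whether it would count as research related or treatment-related is undefined as well.
3. *Non-serious wound infection, possibly related.* It suspends enrollment. Section 7.1 records it as a wound outcome and 9.3 has an infectious category, but nothing says the outcome record feeds the AE numerator.
4. *Serious bleed affecting safety, possibly related.* It suspends enrollment. It is reported within 72 hours whatever its cause, and 9.3 has an SAE group. Whether it counts as treatment-related is still undefined.

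The gap is therefore certain on the text for event 1, wider for event 2, and a matter of unstated counting rules for events 3 and 4.

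**Step 3: size of one omission**

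Inputs: n = 12 (Section 5.1.1); 95% Wilson interval (Section 9.3); z = 1.96, z² = 3.8415. The event count x is an assumption, shown from 0 to 3.

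Limits = [p + z²/2n ± z√(p(1−p)/n + z²/4n²)] / (1 + z²/n), with p = x/n.

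For n = 12: z²/2n = 0.1601, z²/4n² = 0.00667, 1 + z²/n = 1.3201.

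- x = 0: (0.1601 ± 0.1601)/1.3201, giving 0% (0 to 24.2%).
- x = 1: p = 0.0833; root = √(0.00637 + 0.00667) = 0.1142; (0.2434 ± 0.2238)/1.3201, giving 8.3% (1.5 to 35.4%).
- x = 2: 16.7% (4.7 to 44.8%).
- x = 3: 25.0% (8.9 to 53.2%).

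Each omitted subject lowers the reported rate by 1/12 = 8.3 points.

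**The case against.** The strongest reply is that the safeguards overlap. Serious events bearing on safety go to the sponsor and the IRB whatever their attribution. Wound infection and stump revision are recorded regardless of cause (Section 7.1), and infection is assessed from the Day 3 visit to the week 52 call (Table 4). AE/SAE evaluations are scheduled at Visits 2 to 9, and Section 9.3 promises a full case report form. Many Grade 3 events may also meet the seriousness list. All of this stands and narrows the gap. None of it says that an event that triggers suspension enters the AE dataset or the 9.3 numerator, and a general promise about the case report form does not override an explicit exclusion in 10.1.

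It can also be said that a suspension trigger may properly be wider than a summary endpoint. That is true, but the reader of the summary should then be able to see the events that fell between the two, and the plan provides no place for them.

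The exclusion in 10.1 refers to AEs during an enrollment period that is not defined. If that means recruitment only, the exclusion would not reach later events, but the section would then give no collection rule for AEs in follow-up that are not serious.

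A reader might go further than the documents allow in three ways:

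- **That serious stump events could go unreported.** The 72-hour rule has no relatedness condition, so this does not follow.
- **That a suspending infection would leave no trace.** Infection is recorded as an outcome. Only its place in the AE rate is unsettled.
- **That possibly related would be the usual attribution, because every subject has an amputation about a week after injection.** This is plausible, but the documents give no frequency.

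**Conclusion.** The point holds as an inconsistency between event sets. Seriousness is the clearest cause, undefined relatedness the second, and the missing 9.3 categories the third. It is firm for a non-serious Grade 3 bleed or tissue reaction at the index site, including one judged related.

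It would be too strong to say that the sections set conflicting relatedness thresholds: 9.3 neither includes nor excludes possibly related events, because the term is undefined.

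The numerical effect is illustrative. On an assumed single event, the rate moves from 0% to 8.3% and the upper Wilson limit from 24.2% to 35.4%. The documents give no basis for expecting any particular count, and Section 9.3 uses the intervals as description rather than inference, so no decision rule turns on these limits. The point is still worth correcting, because with so few subjects one omitted event decides whether the report shows zero. Section 10.2, listed in the contents as the contact for SAE reporting, was not in the text available, so this rests on the remaining sections.

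**What to change.** Reconcile the three sections as follows.

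1. **Section 10.1:** remove the seriousness condition for collecting and analyzing related AEs. State that every event meeting a 7.3.2 criterion is entered in the AE dataset with its CTCAE grade and relatedness, whether or not it is serious.
2. **One definition of related:** related or possibly related to any research procedure (marrow harvest, BMAC, injection, research biopsy). Use it for the 9.3 numerator, the Wilson intervals and the board tables.
3. **Section 9.3:** add categories for bleeding and local tissue reaction. Say how a wound infection recorded under 7.1 and an event reported under the 72-hour rule enter the numerator.

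The 7.3.2 triggers are left unchanged, and no view is taken on whether they are the right ones.

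The cost is protocol wording, grade and relatedness fields on the AE form, and slightly more data entry. The reported related-AE rate may be less favourable than under the present wording.

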## **8 DATA QUALITY ASSURANCE**

The study site will be responsible for the accuracy of data. Indiana University School of Medicine or its agent may periodically conduct monitoring visits to ensure the quality of data collection.

## **9 STATISTICAL METHODS**

### **9.1 Determination of Sample Size**

The study is not powered for efficacy in preventing wound complications of revision of amputation. The maximum number of tissue specimens we hope to collect will be twelve (12). Quantification of BioCue™, capillary density and cytokines will be compared between injection sites (between escalating doses and control) using a paired Student's t-test. Serum cytokine levels post BioCue™ injection will be compared to baseline levels using a paired Student's t-test.

### **9.2 Bias Minimization**

All subjects meeting the specified eligibility criteria will be enrolled on a first-come basis.

### **9.3 Planned Analyses**

The clinical study report will contain only summary data analyses reflecting safety profiles, and summary data analyses of efficacy. All patient data will remain coded during analyses to maintain patient confidentiality.

The data management center for this trial will be at the CTSI, or a Data Monitoring Committee (DMC) will be appointed by the Principal Investigator. We will use a web-based HIPAA compliant online system for data entry and data management, as we are currently doing in our current clinical trials. Data will be collected from each enrolled patient using a comprehensive case report form and uploaded into a specifically designed database in the OnCore Enterprise Clinical Trial Management System and VA REDCap system. All the data will be analyzed and generated using SAS.

**Safety Assessment.** Primary attention will focus on the safety of the administration of BMAC as measured by treatment-related AEs. Treatment-related AEs will be categorized overlapping systems and severities. Three categories of systems are cardiovascular, respiratory, or infectious. Two categories of severity will be serious adverse (SAE) and major adverse cardiac events (MACE). For completeness, instances of AEs may appear in more than one category. Within each of these categories AEs will be listed in descending order of frequency for the treatment group. In addition, for each category, the sum and difference between the two routes of delivery of the proportions will be reported as percent incidence. Binomial confidence Intervals at the 95% confidence level and *p*-values for these 3 groups will be calculated. Since previous trials have not reported AEs with BMAC treatment, confidence intervals will be generated by the method of the Wilson Score Interval because they are robust, with good coverage probability even for small number of trials and are not degenerate near zero. These intervals will be used to summarize the data rather than as any formal inferential statement and to assist the Data Monitoring Board in their deliberations. No adjustment for multiplicity will be made.

**Exploratory Efficacy.** Continuous confidence intervals at the 95% level will be constructed to explore the effect of administration of BMAC on the composite endpoint at 6-months of death, revision of amputation and gangrene, and will be compared to historical cohorts at our institution. The null hypothesis of no change will be rejected if the pairwise confidence intervals does not include zero. The critical levels for the multiplicity adjustment will be determined by simple Monte Carlo simulation.

Quantities over time of BMAC will be fit to an exponential decay curve using a residual pseudo-likelihood procedure and cell half-life ( $\lambda$ ) will be estimated. Binomial confidence Intervals at the 95% confidence level and *p*-values for these four groups after BMAC transplantation will be calculated for the presence or absence of MHC expression and SDF-1 activation. Continuous confidence intervals at the 95% level will be constructed to explore the differences among the time-tiered administration of BMAC for (1) the CD34+CD133+ pro-angiogenic hematopoietic cells recruitment of HIF-1 $\alpha$ /SDF-1/CXCR4 to ischemic muscle, (2) the quantify of capillary density in muscle fibers using hematoxylin phloxin saffron and CD31 counts, (3) VEGF-A,C,D, hepatocyte growth factor, angiopoietin-1 to characterize angiogenic cytokine expression, (4) percent coverage, fiber diameter and cross-sectional area to examine changes in morphology. The correlation between capillary density (CD31 counts) with tissue perfusion (ICA) for each time point will be estimated by Spearman's rank coefficient.

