**SYNOPSIS**

Title of Study	Safety and efficacy of concentrated autologous concentrated bone marrow aspirate (BMAC) in preventing wound complications in amputations
Objectives	

• Determine the safety and explore efficacy of BMAC in preventing wound complications in amputations.

• Characterize the host tissue response to, paracrine activity of, and fate of transplanted BMAC.

• Determine the effects of chronic limb ischemia and diabetes on nerve function and to assess the effects of mesenchymal stem cell administration on their function.

Planned Number of Subjects and Duration of Involvement	12 patients, 12 month follow up period
Patient Population	Critical limb ischemia (CLI) patients scheduled for amputation
Investigational Product Name	Concentrated autologous bone marrow aspirate (BMAC)
Methodology Overview	
This is an open label pilot trial.
 
Up to twelve (12) patients scheduled for amputation will receive bone marrow cells concentrated (BMAC) via the BioCue™ Platelet Concentration Kit device injected IM at 25 sites in the leg proximal to the amputation in the index limb to prevent ischemic wound complications after surgery. BMAC will be injected into the anterior tibialis muscle (ATM) below the point of amputation for analytical purposes. Patients will be scheduled for amputation at Day 7 post injection. Safety will be evaluated by review of treatment related adverse events (AE) during the 12-month follow-up period. In subjects undergoing BKA, we will compare rates of wound complications and conversion from BKA to AKA to historical controls at our institution to assess trends in therapeutic efficacy.
 
Patients will undergo amputation and injection sites will be harvested from the ATM at that time. Immunohistochemical staining (IHC) will determine capillary density and local host immune responses. Angiogenic and inflammatory cytokines will be quantified using a multiplex array system and quantitative polymerase chain reaction (PCR).

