## **5 STUDY POPULATION**

### **5.1 Sample Size and Target Study Population**

#### **5.1.1 Sample size**

The total number of individual subjects is expected to reach approximately twelve (12).

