#### **6.1.2 Safety issues**

Safety of the BioCue™ device to concentrate BMA for the prevention of wound complications in amputation will be determined by review of treatment related adverse events (AE) and serious adverse events (SAE) during the study period of 12 months by the Data Safety Monitoring Board (DMSB) appointed by the Clinical and Translational Sciences Institute (CTSI) at the Indiana School of Medicine or Data Safety Committee (DMC) designated by the Principal Investigator.

The BMAC dose proposed in this trial was selected based on prior clinical trials. We may not see any evidence of efficacy in our composite endpoint, which may reflect an inadequate dose or sample size. In this case we would propose a future study exploring escalating doses of BMAC. In the instance of evolving infection, we would re-assess our inclusion/exclusion criteria and evaluate the contribution of pre-amputation procedures on the lower leg. Patients may request earlier amputation due to worsening rest pain or anxiety. Consideration for amputation sooner than one week post injections will be determined by the PI based on the severity of the subject's condition, so as to offer this research as an option to all eligible subjects.

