**Determine the safety and explore efficacy of BMAC in preventing wound complications in amputations.** In a Phase I trial, BMAC (up to 3 mL) will be injected into the ATM below the point of amputation in the index limb. At the same time BMAC (1 mL) will be injected at up to 25 sites in the proximal leg to promote tissue perfusion before amputation (**Figure 3, Figure 4**). Patients will be scheduled for amputation approximately one week post-injections. Safety will be evaluated by review of treatment related AEs during the 12-month follow-up period. Efficacy will be assessed by rates of wound complications and revision of amputation to historical controls at our institution to assess trends in therapeutic efficacy.

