## **11** RISK ANALYSIS

### **11.1** Potential Risks of the Investigational Product and Clinical Investigation

The types of risk associated with IM injection are notably rash, mild fever, and myalgia. These risks are mild and rare. These risks are all stated in the consent form.

Further risks include pain, bleeding, and infection following the surgical procedure. Additionally, as with any other surgical procedure, the investigational device may be dropped in the surgical theater. Flash sterilization will not be allowed, and additional sterile devices will be available to prevent procedure termination with minimal delay.

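### Section 9.3 does not report adverse events of the injection-to-amputation week separately, and no scheduled safety laboratory test or ECG falls in that week

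*Combined protocol and SAP*

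**What the plan says.** Safety comes first among the objectives, and section 9.3 measures it as follows: "Primary attention will focus on the safety of the administration of BMAC as measured by treatment-related AEs". That section sorts events into three systems (cardiovascular, respiratory, infectious) and two severity categories (SAE and MACE). It also reports by route of delivery and gives 95% Wilson score intervals, which it describes as a summary and not as formal inference. It names no time period. The window comes from the Synopsis and sections 3, 6.1.2 and 7.1; in the words of 7.1, "Safety will be evaluated by review of treatment related AEs during the 12-month follow-up period".

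The Synopsis sets the timing of surgery: "Patients will be scheduled for amputation at Day 7 post injection". Section 6.1.2 lets this be shortened: "Consideration for amputation sooner than one week post injections will be determined by the PI".

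Table 4 places physical exam, vital signs and AE/SAE evaluation on injection day and on amputation day. It leaves the laboratory and ECG rows blank at both visits and at Day 3. A research blood sample is taken at both operative visits: "Collected prior to induction of surgery (BMAC Injection Day, and Amputation Day) from peripheral vein of up to 30 mL". Missing it is not a protocol deviation.

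Section 11.1 lists the surgical background: "Further risks include pain, bleeding, and infection following the surgical procedure". Section 10.1 says that AEs in the enrollment period go into progress notes but are not collected or analyzed unless the investigator considers them serious and research related.

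**The concern.** The trial is open label with no concurrent control, and every subject is scheduled for major surgery about a week after BMAC. Once the limb is amputated, infection, bleeding and pain are expected in any case, and hsCRP, the only scheduled follow-up laboratory test, can rise from the operation alone. Whether such an event belongs to BMAC then rests on the investigator's unblinded judgement.

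The days between injection and amputation differ in one respect: the amputation has not yet happened. If their events appear only inside a 12-month total, neither a reader nor the monitoring board can see what happened after the BMAC procedure and before the larger operation. If no safety laboratory value or ECG is scheduled then, every scheduled post-injection hsCRP is also a post-amputation hsCRP. The first post-injection ECG is likewise post-surgical, although cardiovascular events and MACE are named reporting categories.

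**Working it through.** The plan gives no precision target or expected event rate for safety, so there is no figure of its own to reproduce.

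**1. Count of assessments after injection (Table 4)**

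| Assessment | Total after injection | Strictly before amputation day | On amputation day | Later |
|---|---|---|---|---|
| Laboratory evaluations | 5 (Weeks 2, 6, 12, 18, 24) | 0 | 0 | 5 |
| 12-lead ECG | 3 (Weeks 2, 12, 24) | 0 | 0 | 3 |

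AE/SAE evaluation has 8 entries: injection day, amputation day and 6 later visits. The amputation-day entry can capture the preceding week, but Table 4 does not say whether it comes before or after the operation.

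**2. Timing of the first safety value.** Section 7.1 counts follow-up weeks from amputation. With amputation at Day 7 and Week 2 at 14 ± 2 days, the first laboratory value or ECG falls at 7 + 12 = Day 19 to 7 + 16 = Day 23 after injection. That is 12 to 16 days after surgery.

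**3. Share of follow-up.** Over the period with scheduled AE visits (to Week 24), 7/(7 + 168) = 7/175 = 4.0%. Over the full window, assuming that Week 52 is also counted from amputation, 7/(7 + 364) = 7/371 = 1.9%. These are shares of time, not of information.

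**4. Precision of a separate early-period table, by the plan's Wilson method.** With p = x/n, n = 12 and z² = 3.8415, the limits are [p + z²/(2n) ± z√(p(1−p)/n + z²/(4n²))] / (1 + z²/n). For x = 0 the upper limit reduces to z²/(n + z²) = 3.8415/15.8415 = 0.2425 (0.24249 before rounding, so 24.2%).

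| Subjects with an event | 95% Wilson interval |
|---|---|
| 0/12 | 0% to 24.2% |
| 1/12 | 1.5% to 35.4% |
| 2/12 | 4.7% to 44.8% |
| 3/12 | 8.9% to 53.2% |

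**5. Chance of seeing at least one event in the early period.** This is 1 − (1 − r)^12 for an assumed true rate r: 46% at r = 5%, 72% at 10%, 93% at 20% and 99% at 30%.

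**6. What pooling hides (assumed rates, independent periods).** Suppose 10% of subjects have an event before amputation and a proportion b have one after it. The pooled rate is 1 − 0.9(1 − b): 28% at b = 20% and 55% at b = 50%. The subjects with an early event are then 0.10/0.28 = 36% and 0.10/0.55 = 18% of those counted, and the pooled figure does not show which they are.

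**7. Sections 9.3 and 10.1 side by side.** Section 9.3 plans to list treatment-related AEs by category and frequency. If the enrollment period in 10.1 means a subject's time on study, 10.1 leaves out every non-serious event, related or not. An early-period table under 10.1 could show 0/12 while mild or moderate reactions sat in progress notes, and the 24.2% limit would bound only serious related events.

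**The case against.** The strongest reply is that the plan already uses this week, and that the week is not clean. Much of that stands.

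- **A reader might infer that the week is ignored.** It is not. Exam, vital signs and AE/SAE evaluation are scheduled on amputation day, and the first three subjects are staggered by at least one week. The suspension rule in 7.3.2 names post-injection as well as post-amputation events. What is missing is separate reporting.
- **A reader might infer that every post-injection blood test follows the amputation.** That holds only for scheduled safety tests. The optional research sample precedes induction on amputation day, and sections 7.1 and 9.1 plan cytokine comparisons with baseline. Section 6.1.3 adds an examination with white count after a positive product culture.
- **A reader might infer that an event in this week can be credited directly to the cells.** The documents do not support that. Marrow harvest and injection form a single operating-room procedure, the ischemic limb is still in place, ulceration or gangrene may be present, and 6.1.2 itself foresees evolving infection and worsening rest pain.
- **The trial is a small descriptive pilot.** This is true and limits the claim. It does not argue against a split that uses dates already needed for the record.
- **Stressing the early week could play down delayed harm at the stump, where BMAC was deliberately injected.** This is a fair warning, and the post-amputation table must keep full weight.

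**Conclusion.** The point holds as a low-cost improvement to how the principal safety objective is reported. Section 9.3 has no breakdown by time relative to amputation, and 0 of 5 laboratory evaluations and 0 of 3 ECGs scheduled after injection come before amputation. The early period speaks to the whole BMAC procedure (harvest, anesthesia and injection together). It is less confounded than later follow-up, but not unconfounded.

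The gain is modest: with 12 subjects an empty early-period table excludes only rates above about 24%, and an event that truly affects 5% of subjects would be missed more often than seen (46% chance of at least one). These figures assume 12 evaluable subjects and complete AE capture. The day counts assume amputation at Day 7, which 6.1.2 allows to be earlier. The value of the split depends on resolving section 10.1.

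**What to change.** 1. **Section 9.3.** Tabulate AEs, with the planned Wilson intervals, in two periods: from injection to the actual start of amputation, and from then to the end of follow-up. Record onset date, and time on amputation day, so that each event can be placed. State that both tables are descriptive, that the first reflects the whole BMAC procedure, and that later stump events are not discounted.
2. **Sections 9.3 and 10.1.** Reconcile which AEs are collected and analyzed, so that the early-period table is not nearly empty by construction.
3. **Table 4.** Add hsCRP and CBC at Visit 3, taken with the pre-induction draw, and list them as scheduled laboratory evaluations so that they do not inherit the optional status of the research sample. Compare with Baseline. Because section 7.1 lets recent clinical values stand in for Baseline tests, running the same assays on the Visit 2 pre-induction draw would give a fresher comparator.
4. **ECG.** State whether the absence of an ECG between injection and amputation is intended, given the cardiovascular and MACE categories.

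The cost is one table split by date, two routine assays at one or two existing blood draws, and smaller counts in each table.
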